6.13.1 Olokizumab Potential Impact on Cytochrome P and Transporter Pathways

Based on nonclinical data (refer to the most recent version of the Investigator’s Brochure), it is possible that OKZ may reverse IL-6-mediated inhibition of CYP or transporter pathways such as CYP1A1/2, 2B6, 2C9, 3A4/5, and 2C19 and sodium/taurocholate co-transporting polypeptide. If CYP or transporter activity is de-suppressed (i.e., increased to any relevant

extent), this may result in decreased level of drugs eliminated by these pathways. As such, OKZ may have clinical relevance for CYP substrates with narrow therapeutic index and for which a change in effectiveness may be undesirable. Investigators are advised to monitor substrates with a narrow therapeutic index (as noted in their respective package inserts/drug labels) and to contact the Medical Monitor to discuss any potential concerns about concomitant medications.

6.13.2 Allowed Medications

The following medications are allowed (non-exhaustive list), including clarifications of the above prohibited medications:

- Inhaled corticosteroids
- Topical corticosteroids
- Oral corticosteroids
 - Doses of ≤ 10 mg/day of prednisone or equivalent are permitted as long as the dose was not changed within the 2 weeks prior to baseline; dose adjustments are not permitted during the study unless the Investigator changes the dose for safety reasons.
- Intra-articular corticosteroids
 - No more than 2 joints may be injected during the study at or after Week 14, after all study assessments for this time point are performed. The cumulative dose for both injections must not exceed 40 mg methylprednisolone or equivalent. Joints treated with IA corticosteroids must be rated with their pre-injection status for the remainder of the study and should be omitted from all subsequent joint assessments (see Sections 7.1.2, 7.1.6, and 7.1.7).
- NSAIDs
 - The subject must have received a stable dose for ≥ 2 weeks prior to baseline, and the dose must be kept constant throughout the entire study unless the Investigator changes the dose for safety reasons.
- Analgesic treatment with paracetamol/acetaminophen is permitted up to a maximum dose of 2000 mg per day (maximum 1000 mg per dose) or up to the maximum dose in the local label, whichever is lower. Paracetamol/acetaminophen are not to be taken within 24 hours prior to joint assessment, including baseline assessment.

6.13.3 Rescue Medication Starting at Week 14

Subjects will be classified in terms of their response to study treatment at Week 14, with nonresponders defined as all subjects who do not improve by at least 20% in both SJC and TJC (66-68 joint assessment). Nonresponders in all groups will be prescribed sulfasalazine and/or hydroxychloroquine according to the local label of the prescribed drug(s) as rescue medication starting at or as close as possible to Week 14, in addition to the assigned study treatment.

The maximum allowed doses of sulfasalazine and hydroxychloroquine are:

- Sulfasalazine: 3 g per day
- Hydroxychloroquine: 400 mg per day

Nonresponders at Week 14 will remain blinded to their assigned treatment. Rescue medication will be administered as open-label treatment. The choice of rescue medication (sulfasalazine, hydroxychloroquine, or both) should be made according to local practice, and the assigned rescue medication regimen should be maintained throughout the study.

For subjects who receive rescue medication, periodic safety evaluations for toxicity resulting from sulfasalazine and/or hydroxychloroquine should be undertaken as per the drug label and local guidelines.

6.14 Medical Treatment for Subjects after End of Study

After completion of the 24-week double-blind Treatment Period, subjects will either roll over into the long-term OLE study or enter the Safety Follow-Up Period. For subjects who complete the study without entering the OLE and for all subjects who discontinue study treatment prematurely, it is the responsibility of the Investigator to choose adequate treatment.

7. EFFICACY, SAFETY, PHARMACOKINETIC, AND HEALTH OUTCOME ASSESSMENTS

7.1 Efficacy Assessments

7.1.1 American College of Rheumatology 20%/50%/70% Response Criteria

ACR20/ACR50/ACR70 will not be calculated by the Investigator during the course of the study, but will be computed in the statistical database for analysis purposes.

The number of subjects who achieve an ACR20, ACR50, or ACR70 response at various time points will be calculated for OKZ and placebo. The calculations are based on a $\geq 20\%$, $\geq 50\%$, and $\geq 70\%$ improvement from baseline in the SJC assessed in 66 joints and in the TJC assessed in 68 joints; and a $\geq 20\%$, $\geq 50\%$, and $\geq 70\%$ improvement from baseline in at least 3 of the 5 remaining core set measures:

- Patient Global Assessment of Disease Activity (VAS).
- Patient Assessment of Pain (VAS).
- HAQ-DI.
- Physician Global Assessment (VAS).
- Level of acute phase reactant (CRP or ESR, using level of CRP in this study).

7.1.2 66-68 Joint Assessment

The 66-68 joint assessment evaluates 66 joints for swelling and 68 joints for tenderness and pain on motion. The hip joints can be assessed for tenderness, but not for swelling. The following joints are included:

- Temporomandibular, sternoclavicular, acromioclavicular, shoulders, elbows, wrists, interphalangeal (IP) on digit 1, distal interphalangeals on digits 2 to 5, proximal interphalangeals (PIP) on digits 2 to 5, metacarpophalangeal (MCP) on digits 1 to 5, hips (tenderness only), knees, ankles and tarsus; metatarsals, IP on toe 1, PIP on toes 2 to 5, and metatarsophalangeals (MTP) on toes 1 to 5.

As noted in Table 1 and Table 2, the joint assessor will be independent to the rest of the study team. An independent joint assessor, blinded to other study assessments as well as the dosing regimen, will be identified at each study site to perform the SJC and TJC. To ensure consistent joint evaluation throughout the study, individual subjects should be evaluated by the same joint assessor for all study visits, whenever possible.

Artificial, missing, and ankylosed joints are excluded from both tenderness and swelling assessments. If joints are missing or not able to be assessed, the number of joints will be weighted by the actual number of assessable joints, and the missing or not assessable joints should be marked as “not assessed” for all subsequent joint assessments for the remainder of the study. If a subject receives intra-articular corticosteroids at or after Week 14 (see Section 6.13), any treated joints should be omitted from all subsequent joint assessments and should be rated with their pre-injection status for the remainder of the study.

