5.3.1 Inclusion Criteria

Subjects may be enrolled in the study only if they meet all of the following criteria:

1. Male or female subjects ≥ 18 years of age
2. Subjects willing and able to sign informed consent
3. Subjects must have a diagnosis of adult-onset RA classified by ACR/EULAR 2010 revised classification criteria for RA (Aletaha et al, 2010) for at least 12 weeks prior to Screening.
 - If the subject was diagnosed according to ACR 1987 criteria previously, the Investigator may classify the subject per ACR 2010 retrospectively, using available source data.
4. Inadequate response to treatment with oral, SC, or intramuscular (IM) MTX (see Section 5.1 for definition of inadequate response to MTX treatment) for at least 12 weeks prior to Screening at a dose of 15 to 25 mg/week (or ≥ 10 mg/week if intolerant to higher doses)
 - The dose and means of administering MTX must have been stable for at least 6 weeks prior to Screening.
5. Subjects must be willing to take folic acid or equivalent throughout the study.
6. Subjects must have moderately to severely active RA disease as defined by all of the following:

- a. ≥ 6 tender joints (68-joint count) at Screening and baseline; and
- b. ≥ 6 swollen joints (66-joint count) at Screening and baseline; and
- c. CRP above ULN at Screening based on the central laboratory results.

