5.4.1.4 Visit 4 (Week 2)

The following assessments will be conducted at Visit 4:

- Administer Patient Global Assessment of Disease Activity (VAS).
- Administer Patient Assessment of Pain (VAS).
- Administer HAQ-DI.
- Perform joint counts (Independent Joint Assessment).
- Record AEs and injection site reactions that have occurred since the previous visit.
- Administer Physician Global Assessment (VAS).
- Record details of contraceptive history/status.
- Record concomitant medications and concomitant non-drug therapies.
- Perform partial physical examination (see Section 7.6.7.1).
- Record vital signs.
- Collect samples to measure CRP level.
- Collect sample for serum biomarkers related to targeted pathway (for subjects included in the sample-rich PK subpopulation only).
- Collect PK sample (see Table 5).
 - For subjects included in the sample-rich PK subpopulation, the PK sample at Visit 4 (Week 2) should be collected prior to study treatment administration (336 ± 24 hours [14 ± 1 days] relative to Visit 2).
 - Subjects in the sample-rich PK subpopulation will return to the study site for the collection an additional blood sample approximately 1 week following Visit 4 (504 ± 24 hours [21 ± 1 days] relative to Visit 2).
- Allocate study treatment through IWRS.

- Administer study treatment.
 - If desired, SC injections may be rotated among the thighs and abdomen.
 - All subjects will remain at the study site for 30 minutes after the injection to be assessed for onset of any systemic injection reactions.

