9.4.6 Multiple Hypothesis Testing

Each of the OKZ treatment groups (64 mg q2w and q4w) will be compared with placebo for each of the primary, secondary, and other endpoints. The overall Type I error rate will be controlled for testing hypotheses of the primary and secondary endpoints at the overall 1-sided $\alpha = 0.025$. The α -control strategy will be based on using the Bonferroni adjustment for the tests related to each of the 2 OKZ dose regimens versus placebo (i.e., using the 1-sided $\alpha = 0.0125$ for each dose). A gate-keeping strategy will be used for tests associated with the primary and secondary endpoints for each OKZ dose regimen independently with the same order of testing as the secondary endpoints are defined above. In other words, each OKZ dose regimen will be tested at 1-sided $\alpha = 0.0125$ for a given endpoint if null hypotheses are rejected at 1-sided $\alpha = 0.0125$ for this dosing regimen for all previous endpoints based on the established order. Conversely, the testing will stop for a given OKZ dose regimen at the endpoint for which the null hypothesis is accepted at 1-sided $\alpha = 0.0125$.

The above multiplicity control procedure will be applied to the primary analysis of the primary and secondary efficacy endpoints based on the ITT population, and will not be applied to sensitivity analyses of these endpoints.

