Missing data may also result from missed intermediate visits for subjects who completed the study. For all binary endpoints, missing intermediate responder status will be imputed from the surrounding visits. If the status at visits both before and after the missed visit is classified as responder, the subject will be considered a responder at the missed visit. Otherwise, the subject will be considered a nonresponder. If an assessment for a given binary endpoint at the last visit is missing for a completing subject, data from the 2 previous visits will be used with the same logic for determining the response status. For the ACR20/50/70 endpoints, if only some components of the response criteria are missing but the available components allow classifying the subject as a responder, the responder category will be used. Otherwise, the method based on surrounding visits as described above will be applied. Similarly, for all continuous endpoints, an average of values from the surrounding visits will be imputed for the missing visit.

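### Read literally, the joint-count rule keeps a temporarily unassessable joint out of every later count, which can move a subject at the threshold across the 20% joint criterion at Week 12

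*Combined protocol and SAP*

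**What the plan says.** Section 7.1.2 first states: "Artificial, missing, and ankylosed joints are excluded from both tenderness and swelling assessments". Its next sentence deals with joints that are missing or cannot be assessed. It rules that "the missing or not assessable joints should be marked as “not assessed” for all subsequent joint assessments for the remainder of the study". The same sentence adjusts the count in such cases: "the number of joints will be weighted by the actual number of assessable joints". No weighting formula is given. Temporary and permanent loss are not distinguished, and no sentence returns a joint to the count. The section's separate instruction on joints injected with corticosteroid applies only at or after Week 14, so it does not bear on Week 12.

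The counts are used as follows:

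- Section 7.1.1 bases ACR20 on at least 20% "improvement from baseline in the SJC assessed in 66 joints and in the TJC assessed in 68 joints", plus at least 20% improvement in 3 of 5 other measures. ACR50 has the same structure.
- Section 5.3.1 requires at least 6 "swollen joints (66-joint count) at Screening and baseline", and likewise at least 6 tender joints.
- The Schedule of Events (Table 1) places joint counts at Weeks 2, 4 and 8 between baseline and Week 12, and at Weeks 12, 14 and 18 before Week 24.
- The 28-joint counts enter DAS28 (CRP) (Section 7.1.6, which points to 7.1.2) and CDAI (Section 7.1.9).

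Section 9.4.9.1 covers missed visits and the case "if only some components of the response criteria are missing but the available components allow classifying the subject as a responder". It does not cover a single joint missing inside a count.

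**The concern.** Carrying not-assessed status forward makes sense for a joint that can never be examined again. The sentence also reaches joints that merely could not be assessed at one visit, for example (my illustration) a wrist under a dressing at Week 4. An assessor who follows the wording would leave that wrist out at Week 12 although it could be examined.

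Percent improvement would then compare a baseline that includes the joint with a follow-up that excludes it. Dropping a joint that is still active creates apparent improvement. Dropping an inactive joint and scaling up the rest can remove real improvement. Both joint counts are mandatory for ACR20 (primary) and ACR50 at Week 24 (gated secondary). The same lost joint also leaves DAS28 (CRP) <3.2 and CDAI ≤2.8: one swollen and tender joint contributes 2 points to a CDAI with a cut-off of 2.8.

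**Working it through.** **1. The plan's own power figures.** Section 9.1 gives 140 per group and Week 12 ACR20 rates of 25% (placebo), 50% (q4w) and 55% (q2w). For DAS28 (CRP) <3.2 it gives 10%, 22% and 30%. Section 9.4.6 tests each regimen "using the 1-sided $\alpha = 0.0125$ for each dose".

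Power = Φ((Δ − z·SE₀)/SE₁), where SE₀ uses the pooled proportion and SE₁ the separate ones. For q4w, z = 2.241, SE₀ = √(2 × 0.375 × 0.625/140) = 0.0579 and SE₁ = √((0.1875 + 0.25)/140) = 0.0559. Then (0.25 − 0.1297)/0.0559 = 2.15, which gives 98.4%. For q2w the result is 99.9%.

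Simulation of 400,000 trials with a shared placebo arm, Bonferroni split and fixed-order gate gives disjunctive power of 99.97% for ACR20 and 98.5% for DAS28. The plan states 100% and 98%, so its figures are reproduced.

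**2. Effect on one subject.** Let B be the baseline swollen count and W the Week 12 count if every joint is examined. Let a = 1 if the lost joint is still swollen at Week 12, and a = 0 if not. Assume proportional weighting.

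- Joint examined: (B − W)/B.
- Joint dropped: (B − (W − a) × 66/65)/B.

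| B | W | a | Examined | Dropped | 20% criterion |
|---|---|---|---|---|---|
| 6 | 5 | 1 | 1/6 = 16.7% | (6 − 4.06)/6 = 32.3% | not met → met |
| 10 | 8 | 0 | 2/10 = 20.0% | (10 − 8.12)/10 = 18.8% | met → not met |
| 6 | 6 | 1 | 0% | (6 − 5.08)/6 = 15.4% | unchanged |

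Without weighting, the first row would show 33.3% and the second would stay at 20.0%.

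**3. How general this is.** I enumerated every baseline count from 6 to 40. Each has exactly one Week 12 count at which losing one joint changes the criterion. For 22 of the 35 baseline counts a still-active lost joint turns non-response into response (6 to 5, 9 to 8, 12 to 10). For the other 13 an inactive lost joint does the reverse (10 to 8, 15 to 12, 20 to 16). The 68-joint tender count, scaled by 68/67, gives the same 22 and 13. Without weighting, all 35 have a flip to response.

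**4. Would matching the joint sets repair it?** Only in part.

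- 6 to 5, still-swollen joint removed at both visits: 5 to 4, exactly 20.0%, which still meets the criterion.
- 10 to 8, lost joint never swollen: stays 10 to 8, 20.0%, repaired.
- 10 to 8, lost joint swollen at baseline but resolved: 9 to 8, 11.1%, further from the true 20.0% than the 18.8% in the table.

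**5. Trial level, by assumption.** The documents give no frequency of temporary non-assessability. If 1% to 3% of 420 subjects had one such joint before Week 12, 4 to 13 would carry an altered count (420 × 0.01 = 4.2; 420 × 0.03 = 12.6). If 2% to 10% of those changed responder status, that is about 0.1 to 1.3 subjects (4.2 × 0.02 = 0.08; 12.6 × 0.10 = 1.26).

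As a wider test, let 1% to 20% of subjects lose a joint and 2% to 10% of the non-responders among them flip to response, equally in all arms. At the extreme the rates become:

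- placebo: 0.25 + 0.75 × 0.20 × 0.10 = 26.5%
- q4w: 0.50 + 0.50 × 0.02 = 51.0%
- q2w: 0.55 + 0.45 × 0.02 = 55.9%

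Over the whole range, power is 97.9% to 98.4% for q4w and 99.8% to 99.9% for q2w, a loss of about 0.5 points at most.

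**The case against.** The strongest reply is that the sponsor meant only permanent loss. The sentence repeats the word missing, so it can be read as the operating rule for the joints named just before it, and a carry-forward to study end fits permanent conditions. The wording is also should, not must. That reading is possible. However, the sentence adds joints that cannot be assessed, sets no limit, and follows one that already deals with structural loss. Assessors need wording that settles the question.

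Second, 66/65 is my assumption, and Section 9.4 leaves analysis details to an SAP finalised before unblinding. That stands: a later derivation could match the joint sets. But it could not recover a finding the assessor never recorded.

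Third, few subjects would be affected. That also stands. ACR20 changes only for a subject at the joint threshold whose other joint count and 3 of 5 further measures already qualify. Both worked flips are threshold cases chosen to show the mechanism.

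A reader might go further and infer a biased treatment comparison or an underpowered trial. The documents support neither. Joint assessors are independent and blinded to regimen and to other assessments (Sections 6.12 and 7.1.2), the errors run in both directions, and the power effect is negligible. Nor are the 4 to 13 subjects in the working misclassified responders; they are altered counts under an assumed frequency.

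**Conclusion.** The point holds as a defect in a measurement rule. On its literal wording, Section 7.1.2 discards a joint that may be examinable at Week 12, and nothing else in the documents restores it or aligns the baseline count. For a subject at the threshold, one joint can change the 20% criterion in either direction. The direction and size rest on proportional weighting; without weighting, every flip is toward response.

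The documents do not establish that assessors would in fact drop examinable joints, only that the wording tells them to if read as it stands. Frequency is unknown, the likely number of changed ACR20 classifications is very small, and study power is essentially untouched. The change is still worth making, because the misclassification falls on the primary and the joint-based gated secondary endpoints and costs almost nothing to avoid.

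**What to change.** In Section 7.1.2, confine the carry-forward of not-assessed status to joints that are permanently unassessable: artificial, missing or ankylosed. State that any other joint which cannot be assessed at a visit is recorded so for that visit only and is examined again at the next. This removes the error for every joint that is examinable again by Week 12 or Week 24.

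As a secondary point, state the weighting formula and which joints the baseline count uses when a joint is absent at follow-up. Matching the sets is a convention worth fixing in advance, but it is only a partial repair and does not replace re-examination.

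The cost is one protocol sentence, a matching line in the assessor instructions and one derivation line in the SAP. No visits, staff or subjects are added.

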7.1.3 Patient Global Assessment of Disease Activity (Visual Analog Scale)

Subjects will assess the overall disease activity by responding to the following:

- Considering all the ways in which illness and health conditions may affect you at this time, please make a mark below to show how you are doing, using a 100 mm VAS where 0 is “very well” and 100 is “very poorly.”

7.1.4 Patient Assessment of Pain (Visual Analog Scale)

Subjects will rate their level of short-term arthritis pain by responding to the question:

- How much pain are you experiencing because of your illness AT THIS TIME? Place a vertical (I) mark on the line to indicate the severity of the pain, using a 100 mm VAS where 0 is “no pain” and 100 is “severe pain.”

7.1.5 Physician Global Assessment (Visual Analog Scale)

The Investigator will rate the overall status of the subject for the day of the visit, with respect to RA signs and symptoms and the functional capacity of the subject. The Investigator will respond to the following:

- Mark an X on the line below to indicate disease activity (independent of the patient’s self-assessment). A 100 mm VAS will be used, where 0 is “no disease activity” and 100 is “maximal disease activity.”

7.1.6 Disease Activity Score 28-Joint Count (C-Reactive Protein)

The DAS28 (CRP) will not be calculated by the Investigator during the course of the study, but will be computed in the statistical database for analysis purposes. The DAS28 (CRP) will be kept blinded after Screening.

The DAS28 (CRP) will be calculated using the SJC (28 joints), TJC (28 joints), CRP level, and the Patient Global Assessment of Disease Activity (VAS) (in mm) according to the following formula:

$$\text{DAS28 (CRP)} = 0.56 \times \sqrt{\text{TJC}} + 0.28 \times \sqrt{\text{SJC}} + 0.36 \times \log_{\text{nat}}(\text{CRP} + 1) + 0.014 \times \text{Patient Global Assessment of Disease Activity (VAS)} + 0.96$$

The 28 joints evaluated for the SJC and TJC are as follows:

- Shoulders, elbows, wrists, IP on digit 1, PIP on digits 2 to 5, MCP on digits 1 to 5, and knees.

Details of the joint assessment process are provided in Section 7.1.2.

7.1.7 Disease Activity Score 28-Joint Count (Erythrocyte Sedimentation Rate)

The DAS28 (ESR) will not be calculated by the Investigator during the course of the study, but will be computed in the statistical database for analysis purposes. The DAS28 (ESR) will be kept blinded after Screening.

The DAS28 (ESR) will be calculated using the SJC (28 joints), TJC (28 joints), ESR (mm/hour), and the Patient Global Assessment of Disease Activity (VAS) (in mm) according to the following formula:

$$\text{DAS28 (ESR)} = 0.56 \times \sqrt{\text{TJC}} + 0.28 \times \sqrt{\text{SJC}} + 0.70 \times \log_{\text{nat}}(\text{ESR}) + 0.014 \times \text{Patient Global Assessment of Disease Activity (VAS)}$$

The 28 joints evaluated for the SJC and TJC are as follows:

- Shoulders, elbows, wrists, IP on digit 1, PIP on digits 2 to 5, MCP on digits 1 to 5, and knees.

Details of the joint assessment process are provided in Section 7.1.2.

